	
immunogenicity data obtained within the study visit windows at Day 211.
 
The primary and other immunogenicity endpoints will be analyzed using the mITT population. Sensitivity analyses on immunogenicity data will also be presented using the PP population.
 
Immunogenicity will be measured by serum rF1V [REDACTED] concentration at each visit.
 
The administration method of vaccine utilized in Part 2 of the study will be selected after Day 57 immunogenicity data become available to determine whether the GMC 1 month after 2 doses of rF1V vaccine with CpG 1018 using the selected administration method is at least 2 times higher than that 1 month after 2 doses of rF1V vaccine in Group 3.
 
[REDACTED] threshold that corresponds to 50% predicted vaccine efficacy after 2 doses of rF1V vaccine with CpG 1018 will be obtained from a model using [REDACTED] data after 3 doses of rF1V vaccine (or after 2 doses of rF1V with CpG 1018 TBD) in this study. The threshold and the model used will be described in a separate report.
 
Predicted protection rate (percentage of subjects reaching the [REDACTED] threshold) and associated 95% two-sided Clopper-Pearson confidence intervals will be computed. Fisher's exact tests will be used to compare predicted protection rate between study groups.
 
The criterion for evaluation of the primary endpoint 1 in Part 2 is: a similar percentage of subjects reaching the [REDACTED] threshold that corresponds to 50% predicted vaccine efficacy after 2 doses of rF1V vaccine with CpG 1018 as compared to that after 3 doses of rF1V vaccine.
 
The criterion for evaluation of the primary endpoint 2 in Part 2 is: 2-times increase of [REDACTED] GMC point estimate after the second dose of rF1V vaccine with CpG 1018 compared to that after rF1V vaccine.
 
Criteria for secondary objectives are GMC and seroconversion rate point estimates from rF1V vaccine with CpG 1018 to meet or exceed results from rF1V vaccine at relevant visits
 
Safety data will be analyzed descriptively and will be based on the Safety Population. Summary statistics will be used to describe the incidence of all post-injection reactions, AEs, AESIs, SAEs, and deaths. Tables of adverse events will include incidence, severity, seriousness, and relationship to the investigational vaccines.
 
Data from Part 1 subjects and Part 2 subjects will be combined to evaluate the Part 2 objectives.

--	--

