11.1 Sample Size Considerations

Part 2 primary objective 1 is to assess the utility of a 2-dose schedule of rF1V vaccine with CpG 1018 as measured by reduction in time to onset of predicted rF1V protection. The predicted protection will be based on a [REDACTED] titer threshold. Previous animal studies have established protective efficacy in animals. Since a human efficacy study is not feasible, an immunobridge from animal data to human data via the [REDACTED] test will be used to predict the protective efficacy in humans using a regression model. An initial predicted protection threshold will be calculated based on the data generated in this study in Group 3 after 3 doses of rF1V vaccine. Once the threshold is identified, it will be applied to the study groups in Part 2 of the study to evaluate the objectives. In addition to the previous animal studies conducted to establish protective efficacy, a new animal model utilizing rF1V vaccine with CpG 1018 will be developed to establish the protective level of antibody for CpG 1018 containing vaccines. Additional analyses will include a predicted protection threshold that will be calculated based on the data generated under the new animal model after 2 doses of rF1V vaccine with CpG 1018. In both instances, the animal-to-human immunobridge and the identification of the predicted protection thresholds will be documented in a separate report.

A similar approach was used to analyze the previous Phase 2a and Phase 2b study data using the animal model from the previous animal studies. Thresholds that corresponded to 50% predicted protective efficacy in humans were established for those trials. In a pooled analysis of these previous immunobridge studies, 93% (95% Clopper Pearson confidence interval [CI] = 85%, 98%) of subjects reached the predicted protection threshold.

It is assumed that a similar percentage of the subjects in Group 3 will reach the threshold identified in this study. When this threshold is applied to both Part 2 study groups, a similar

lower bound of the 95% CI is desired across the groups. Table 11-1 shows the lower bound of 95% Clopper Pearson CI for different observed levels of predicted protection assuming 85 of the 90 planned subjects (Part 1 N = 20 and Part 2 N =70) will have data available for the evaluation. Thus, with a predicted protection level of 93%, the lower bound of the 95% CI would be 85%.

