4.0 SAMPLE SIZE CONSIDERATIONS

Part 2 primary objective 1 is to assess the utility of a 2-dose schedule of rF1V vaccine with CpG 1018 as measured by reduction in time to onset of predicted rF1V protection. The predicted protection will be based on a [REDACTED] meter threshold. Previous animal studies have established protective efficacy in animals. Since a human efficacy study is not feasible, an immunobridge from animal data to human data via the [REDACTED] test will be used to predict the protective efficacy in humans using a regression model. An initial predicted protection threshold will be calculated based on the data generated in this study in Group 3 after 3 doses of rF1V vaccine. Once the threshold is identified, it will be applied to the study groups to evaluate the Part 2 objectives. In addition to the previous animal studies conducted to establish protective efficacy, a new animal model utilizing rF1V vaccine with CpG 1018 will be developed to establish the protective level of antibody for CpG 1018 containing vaccines. Additional analyses will include a predicted protection threshold that will be calculated based on the data generated under the new animal model after 2 doses of rF1V vaccine with CpG 1018. In both instances, the animal-to-human immunobridge and the identification of the predicted protection thresholds will be documented in a separate report.

A similar approach was used to analyze the previous Phase 2a (NCT00332956) and Phase 2b (NCT01122784) study data using the animal model from the previous animal studies. Thresholds that corresponded to 50% predicted protective efficacy in humans were established for those trials. In a pooled analysis of these previous immunobridge studies, 93% (95% Clopper Pearson confidence interval [CI] = 85%, 98%) of subjects reached the predicted protection threshold.

It is assumed that a similar percentage of the subjects in Group 3 will reach the threshold identified in this study. When this threshold is applied to both Part 2 study groups, a similar lower bound of the 95% CI is desired across the groups. Table 4-1 shows the lower bound of 95% Clopper Pearson CI for different observed levels of predicted protection assuming 85 of the 90 planned subjects (Part 1 N = 20 and Part 2 N =70) will have data available for the evaluation. Thus, with a predicted protection level of 93%, the lower bound of the 95% CI would be 85%.

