7.0 TIMING OF ANALYSES

The administration method of vaccine utilized in Part 2 of the study will be selected by Dynavax in consultation with the Department of Defense (DoD) after Day 57 immunogenicity data in Part 1 subjects become available. The evaluation will be based on unblinded data. Blinding will be retained for those who are blinded per study requirements throughout the study.

Final analyses will be carried out after the last participant has completed their last study visit, the study database has been authorized by Dynavax as complete and final, and major protocol deviations have been identified.

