8.6 Immunogenicity Analyses

The primary and other immunogenicity endpoints will be analyzed using the mITT population. Sensitivity analyses on immunogenicity data will also be presented using the PP population.

Immunogenicity will be measured by serum rF1V [REDACTED] concentration at each visit.

Data from Part 1 subjects and Part 2 subjects will be combined to evaluate the Part 2 objectives. No multiplicity adjustment is proposed.

Additional analyses may be attempted, including analysis to quantify antibody decay over time.

Part 1 Primary Objective: To select one of the two methods of administration of rF1V vaccine with CpG 1018 for Part 2 by comparing humoral immunization response 28 days after the second dose of vaccine

Endpoint: Ratio of geometric mean ELISA concentrations (GMCs) between rF1V vaccine with CpG 1018 and rF1V vaccine.

Estimand: GMCs and associated two-sided 95% confidence intervals for each of the 3 study groups will be computed by exponentiating the mean and associated Student's t confidence interval of the log10 transformed individual antibody concentrations assuming Normal distribution. The ratio of GMCs and associated two-sided 95% confidence interval will be compared between rF1V vaccine with CpG 1018 and rF1V vaccine, using Student's t method. The ratio of GMCs and associated two-sided 95% confidence interval between two administration methods of rF1V vaccine with CpG 1018 vaccines will also be produced.

Criterion for evaluation: GMC 1 month after 2 doses of rF1V vaccine with CpG 1018 using the selected administration method is at least 2 times higher than that 4 weeks after 2 doses of rF1V vaccine.

Part 2 Primary Objective 1: To assess the utility of a 2-dose schedule of rF1V vaccine with CpG 1018 as measured by reduction in time to onset of predicted rF1V protection

Endpoint: Predicted protection (percentage of subjects reaching the [REDACTED] threshold that corresponds to 50% predicted vaccine efficacy) at Week [REDACTED] after 2 doses of rF1V vaccine with CpG 1018 as that at Week [REDACTED] after 3 doses of rF1V vaccine without CpG 1018. The [REDACTED] threshold that corresponds to 50% predicted vaccine efficacy will be obtained from a model using [REDACTED] data after 3 doses of rF1V vaccine (or after 2 doses of rF1V

with CpG 1018 TBD) in this study. The threshold and the model used will be described in a separate report. Part 2 Primary Objective 1 can only be evaluated after the determination of this threshold.

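### Part 2 primary endpoint 1: the SAP and protocol disagree on which data set the primary protection threshold, and neither requires the method to be fixed before Part 2 unblinding

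*SAP*

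**What the plan says.** **Source of the threshold.** SAP 8.6, Part 2 Primary Objective 1, obtains the threshold from a model that uses titres after three doses of rF1V, or alternatively after two doses "with CpG 1018 TBD) in this study. The threshold and the model used will be described in a separate report". The Statistical Methods part of the protocol synopsis has the same choice: "data after 3 doses of rF1V vaccine (or after 2 doses of rF1V with CpG 1018 TBD) in this study".

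SAP 4.0 carries no such choice for the main threshold: "An initial predicted protection threshold will be calculated based on the data generated in this study in Group 3", after three doses. Protocol 11.1 uses the same sentence and continues: "Once the threshold is identified, it will be applied to the study groups in Part 2 of the study to evaluate the objectives". Both sections then give the CpG-based threshold a different role: "Additional analyses will include a predicted protection threshold that will be calculated based on the data generated under the new animal model". Both say that the two thresholds will be documented in a separate report.

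**Timing.** SAP 8.6 has one sequencing rule: "Part 2 Primary Objective 1 can only be evaluated after the determination of this threshold". SAP 7.0 says "Final analyses will be carried out after the last participant has completed their last study visit", and adds two further conditions: a final database and identified major deviations. The threshold, its model and the separate report are not among them. For the Part 1 choice of administration method, SAP 7.0 says "The evaluation will be based on unblinded data", and the next sentence keeps the blind for those who are blinded under the study requirements.

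**The concern.** The threshold turns a continuous titre into the responder status on which primary endpoint 1 rests. If its source is open in one section and settled in another, two analysts working from different sections could compute different primary results from the same titres. If the source and model may also be settled after titres are known by group, the cut-off can be chosen in the light of the result, even without any intent to do so. A reader of the final report could not then tell a pre-specified threshold from a selected one.

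**Working it through.** **1. The plan's own figures.** The Clopper-Pearson 95% limits for x of n are the 0.025 quantile of Beta(x, n−x+1) and the 0.975 quantile of Beta(x+1, n−x). With n = 85:

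- 81/85 = 95.3%: 88.4 to 98.7
- 79/85 = 92.9%: 85.3 to 97.4
- 77/85 = 90.6%: 82.3 to 95.8

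All agree with SAP Table 4-1 and protocol Table 11-1 after rounding. Nothing numerical in the plan is wrong here.

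**2. The passages side by side.**

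| Place | Source of the threshold for the primary endpoint | Role of the CpG-based threshold |
|---|---|---|
| SAP 4.0, protocol 11.1 | Group 3 after three doses, called initial | Additional analysis, using the new animal model |
| SAP 8.6, synopsis | Three-dose rF1V data, or two-dose CpG data, undecided | Possible primary source |

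The word initial leaves some room for revision. It does not move the CpG-based threshold out of the additional analyses, so the two rows cannot both hold.

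**3. Timing.** Threshold before evaluation of the objective is required. Threshold method before unblinding is not. SAP 8.2 orders steps around database lock and unblinding for per-protocol membership, so the SAP uses such ordering elsewhere.

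**4. What the Part 1 look reveals.** Day 57 is Week 8, the endpoint time for the CpG group (SAP 4.0, text after Table 4-1). Part 1 data are pooled into the Part 2 objectives (SAP 8.0). The look therefore covers 20/90 = 22% of the planned CpG endpoint values. At a true rate of 93%, 20 values have a standard error of √(0.93 × 0.07 / 20) = 5.7 points. Group 3's endpoint is Week 30, so the look contains none of its endpoint values.

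**5. Illustration of size.** The documents give no titre spread, no second cut-off and no margin for similarity, so these inputs are assumed:

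- Log titres are normal with equal SD, and n = 85 per arm.
- Cut-off A is the fixed point that 93% of Group 3 exceeds. Cut-off B is 0.25 or 0.5 SD lower or higher.
- Success means that the CpG lower confidence bound is at most 5 points below Group 3's.
- There are 200,000 simulated trials per case.

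| CpG mean minus Group 3 mean | Success at A | Success at B (four shifts) | A and B disagree |
|---|---|---|---|
| −0.5 SD | 13.5% | 4 to 40% | 10 to 32% |
| −0.3 SD | 42% | 24 to 67% | 21 to 36% |
| 0 | 85% | 77 to 91% | 12 to 20% |
| +0.5 SD | 99.6% | 99.5 to 99.8% | under 1% |

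If the 5-point margin is put on the observed percentages instead, disagreement is about 14 to 44% at −0.5 SD and 7 to 16% at 0. Under the lower-bound rule, being free to pick the better cut-off adds at most 6 points over the better single cut-off. Most of the difference comes from where the bar is set.

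**6. A check without a margin.** Assume a log10 SD of 0.3 and a CpG two-dose GMC that is 0.67 times the Group 3 three-dose GMC. Cut-off A lies 1.476 × 0.3 = 0.443 below the Group 3 log10 mean, and log10(0.67) = −0.174.

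- At A: the CpG rate is Φ((0.443 − 0.174)/0.3) = 81.5%. Expected counts are 69/85 against 79/85, Fisher p = 0.038.
- At half of A (a further 0.301 lower, or 1 SD): expected counts are 83/85 against 84/85, p = 1.0.

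With a log10 SD of 0.45 or 0.6, Fisher's test is non-significant at both cut-offs (p = 0.212 and 0.621; 0.432 and 0.682). The reversal therefore depends on the spread.

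**The case against.** The case on the other side has several sound parts.

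- **Blinding is not absent.** Protocol 9.3 has the immunogenicity assays run blinded, SAP 7.0 keeps the blind for those who are blinded, and SAP 8.2 implies that assignments are revealed after database lock. All of this stands, but none of it fixes the threshold method first.
- **Both thresholds appear to be planned.** A reader might infer that one will be dropped or hidden. The documents do not support that, since SAP 4.0 and protocol 11.1 announce both. What is unsettled is which one is primary.
- **The two descriptions of the CpG source may be compatible.** SAP 8.6 speaks of data in this study and SAP 4.0 of the new animal model. An animal-to-human bridge needs both kinds of data, so this contrast alone is weak evidence of conflict.
- **The Part 1 look is limited.** A reader might infer that it shows the primary comparison before the cut-off is set. It does not, because Group 3's Week 30 values are not part of it.
- **The separate report may contain a lock.** It is not among the documents. The point is that neither the protocol nor the SAP requires one.
- **The value cannot be fixed in advance.** A threshold built on Group 3 data needs group-level data. That is correct, but the source, model and algorithm can be fixed beforehand.
- **Without a margin for similarity there is no formal verdict to reverse.** This is fair as to size. It does not remove the conflict over how the endpoint is defined.

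**Conclusion.** The concern holds in this form: SAP 8.6 and the synopsis leave the source of the primary threshold undecided, SAP 4.0 and protocol 11.1 settle it, and no supplied text requires the method to be fixed before Part 2 unblinding. The missing lock is the main risk; the Part 1 look is a minor one.

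The size cannot be computed from the documents. The disagreement rates rest on the assumed 5-point margin, the assumed shifts between cut-offs, equal SDs and a cut-off A treated as fixed, although the plan estimates it from Group 3. They show that the choice can matter when the CpG response is similar or somewhat lower, and hardly matters when it is clearly higher. The conclusion rests on the text, not on these rates.

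It would go too far to say that the cut-off will be chosen to favour a result, or that free choice would greatly inflate the chance of success. The documents show no such intent, and the illustration gives a gain of at most 6 points over the better single cut-off.

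**What to change.** 1. **SAP 8.6:** delete the bracketed alternative. Name the threshold from Group 3 and the existing animal model as primary, in line with SAP 4.0 and protocol 11.1, and keep the CpG-model threshold as the additional analysis already planned. If the sponsor prefers the CpG source as primary, SAP 4.0, SAP 8.6, protocol 11.1 and the synopsis must all say so before unblinding.
2. **SAP 7.0:** add: *The threshold method (data source, model, algorithm) is signed and dated before Part 2 titres are unblinded by group; the Group 3 value is then computed by that fixed method.*
3. **Sensitivity analysis:** repeat primary endpoint 1 in Part 2 subjects only (70 planned per arm), which leaves out the values seen in the Part 1 look.

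**Cost.** One dated method document is needed, and under the default choice the CpG-model threshold is supportive only in this trial. The synopsis is protocol text, so aligning it needs an amendment with IRB approval (protocol section 13). The SAP edits alone remove most of the risk. The missing margin for similarity is a separate issue that these changes do not resolve.

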In the Dynavax study HBV-10 of adults 18 to 55 years of age, the SPR at four weeks after the second dose of HEPLISAV-B, at week 8, was statistically significantly higher than the SPR in the Engerix-B group at week 8 (88.4% vs 26.7%, $p < 0.0001$). It was also significantly higher than the peak SPR following three doses of Engerix-B at week 28 (81.3%, $p < 0.001$). At week 8, the geometric mean concentration (GMC) of anti-HBs antibodies was 83.1 mIU/mL in the HEPLISAV-B group and 6.5 mIU/mL in the Engerix-B group ($p < 0.0001$). The peak GMC in the HEPLISAV-B group (341.6 mIU/mL) was similar to the peak GMC in the Engerix-B group (352.1 mIU/mL).

In summary, the CpG 1018 adjuvanted HBV vaccine, HEPLISAV-B, with a 2-dose regimen administered within 1 month induced a peak SPR, GMC, as well as duration of response greater than or similar to what was seen after 3 doses of Engerix administered over 6 months. The improved dosing schedule achieved by adjuvating HBsAg with CpG 1018 is comparable to the goal identified by the Military in this prototype project, namely accelerating the onset of protection and a non-inferior or superior immunological response to rF1V antigen in a dramatically shortened vaccination schedule.

Safety data are available for 9365 adult participants who received CpG 1018 in the three phase 3 HEPLISAV-B pivotal trials (HBV-23, HBV-16, and HBV-10) and 31,000 HEPLISAV-B recipients in a post-marketing study. In addition, over 900,000 doses of HEPLISAV-B have been distributed in the US since 2017 with benign spontaneous safety reports both to the Vaccine Adverse Events Reporting System (VAERS) and Dynavax.

HEPLISAV-B induces a similar frequency of local post-injection reactions (PIRs) and a lower frequency of systemic PIRs (including fever) compared to Engerix-B. Overall, 55.1% of subjects in the HEPLISAV-B arm experienced any PIR compared to 57.1% of subjects in the Engerix-B arm. Systemic PIRs occurred in 32.3% of the HEPLISAV-B group and 37.4% of the Engerix-B group, and local PIRs occurred in 42.8% of the HEPLISAV-B group and 41.1% of the Engerix-B group. Adverse events, serious adverse events, immune-mediated adverse events of special interest, and deaths were balanced between the HEPLISAV-B and Engerix-B groups. Changes in autoantibodies including ANA, anti-dsDNA, and ANCA were similar between vaccine groups ([Hyer, McGuire et al. 2018](#)).

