11.4 Immunogenicity Endpoints

The primary and other immunogenicity endpoints will be analyzed using the mITT population. Sensitivity analyses on immunogenicity data will also be presented using the PP population.

Immunogenicity will be measured by serum rF1V [REDACTED] concentration at each visit.

Part 2 Primary Objective 1: To assess the utility of a 2-dose schedule of rF1V vaccine with CpG 1018 as measured by reduction in time to onset of predicted rF1V protection

Endpoint: predicted protection (percentage of subjects reaching the [REDACTED] threshold that corresponds to 50% predicted vaccine efficacy) at Week 8 after 2 doses of rF1V vaccine with CpG 1018 as that at Week 30 after 3 doses of rF1V vaccine without CpG 1018

[figure not shown]
Percentage of subjects reaching the [REDACTED] threshold and associated 95% two-sided Clopper-Pearson confidence intervals will be computed. Fisher's exact tests will be used to compare predicted protection rate between study groups.

Criterion for evaluation: similar percentage of subjects reaching the [REDACTED] threshold that corresponds to 50% predicted vaccine efficacy after 2 doses of rF1V vaccine with CpG 1018 as compared to that after 3 doses of rF1V vaccine.

Part 2 Primary Objective 2: To assess the serum [REDACTED] concentration to rF1V vaccine with CpG 1018 compared with rF1V vaccine 28 days after the second dose of vaccine

Endpoint: Ratio of geometric mean ELISA concentration (GMC) between rF1V vaccine with CpG 1018 and rF1V vaccine at Week [REDACTED]

Criterion for evaluation: 2-times increase in [REDACTED] GMC point estimate after the second dose of rF1V vaccine with CpG 1018 to that after the second dose of rF1V vaccine.

Criteria for secondary objectives are GMC and seroconversion rate point estimates from rF1V vaccine with CpG 1018 to meet or exceed results from rF1V vaccine at relevant visits.

Data from Part 1 subjects and Part 2 subjects will be combined to evaluate the Part 2 objectives. No multiplicity adjustment is proposed as the Part 1 objectives are not evaluated against the 3-dose regime control group.

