Table 4-1: Precision Estimate at Various Level of Predicted Protection Using Clopper Pearson CI (N=85)

Predicted Protection Level	Lower Bound of 95% CI	Upper Bound of 95% CI
95%	88%	99%
93%	85%	97%
91%	82%	96%

When the lower bound of 95% CI for the predicted protection after 2 doses of rF1V vaccine with CpG 1018 (ie, at Week 8) is similar to that after 3 doses of rF1V vaccine (ie, at Week 30), the reduction of onset time to predicted rF1V protection is demonstrated.

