Estimand: Percentage of subjects reaching the [REDACTED] threshold and associated 95% two-sided Clopper-Pearson confidence intervals will be computed. Fisher's exact tests will be used to compare predicted protection rate between study groups.

Criterion for evaluation: Similar percentage of subjects reaching the [REDACTED] threshold that corresponds to 50% predicted vaccine efficacy after 2 doses of rF1V vaccine with CpG 1018 as compared to that after 3 doses of rF1V vaccine.

Part 2 Primary Objective 2: To assess the serum [REDACTED] concentration to rF1V vaccine with CpG 1018 compared with rF1V vaccine 28 days after the second dose of vaccine

Endpoint: Ratio of geometric mean ELISA concentration (GMC) between rF1V vaccine with CpG 1018 and rF1V vaccine at Week [REDACTED].

Estimand: GMCs and associated two-sided 95% confidence intervals will be computed by exponentiating the mean and associated Student's t confidence interval of the log10 transformed individual antibody concentrations assuming Normal distribution. The ratio of GMCs and associated two-sided 95% confidence interval will be compared between rF1V vaccine with CpG 1018 and rF1V vaccine, using ANOVA if site can be used as an adjustment factor in the model or Student's t method.

Criterion for evaluation: 2-times increase in [REDACTED] GMC point estimate after the second dose of rF1V vaccine with CpG 1018 to that after the second dose of rF1V vaccine.

Part 2 Secondary Objective: To assess the serum [REDACTED] concentration to rF1V with CpG 1018 at selected time points after each dose

Endpoint: GMC and seroconversion rate of serum rF1V [REDACTED] titers at the following selected time points after each dose of vaccine:

- [REDACTED]

- [REDACTED]

[figure not shown]
Seroconversion is defined as the presence of detectable antibody in subjects who had no detectable antibody levels at Day 1, or a 2: 2-fold increase in antibody level in subjects who had detectable antibody levels at Day 1.

Estimand: GMCs and associated two-sided 95% confidence intervals will be computed by exponentiating the mean and associated Student's t confidence interval of the log10 transformed individual antibody concentrations assuming Normal distribution.

Seroconversion rate and associated 95% two-sided Clopper-Pearson confidence intervals will be computed.

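### Part 2 primary objective 1 turns on an undefined 'similar': no margin, no interval for the difference, and no rule on whether the Fisher test or the single-arm lower bounds decide

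*SAP*

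**What the plan says.** The documents contain two statements on how this objective is judged.

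- **Analysis sections.** SAP 8.6 reads "Criterion for evaluation: Similar percentage of subjects reaching the" threshold, and Protocol 11.4 has the same criterion: "Criterion for evaluation: similar percentage of subjects reaching the" threshold. Neither attaches a number. The planned methods are a 95% Clopper-Pearson interval for the percentage, and Fisher's "exact tests will be used to compare predicted protection rate between study groups". Neither section says what a significant or non-significant Fisher result means for the conclusion.
- **Sample-size sections.** SAP 4.0 and Protocol 11.1 say that "a similar lower bound of the 95% CI is desired across the groups". After the precision table they add that, when the Week 8 and Week 30 lower bounds are similar, "the reduction of onset time to predicted rF1V protection is demonstrated". Again there is no number.

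No margin and no interval for the between-group difference appears in either document. The redactions in these sentences fall where an assay label, threshold label or visit day would stand; the criterion wording is readable.

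**The concern.** The claim is one of similarity, in effect non-inferiority of the shorter schedule. Protocol 2.4.2.1.1 describes the project's goal as "a non-inferior or superior immunological response to rF1V antigen in a dramatically shortened vaccination schedule". Fisher's exact test looks for a difference, so failing to find one in 85 subjects per arm cannot support that claim.

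The lower-bound statement does not fill the gap. With equal numbers per arm, a Clopper-Pearson lower bound is an increasing function of the observed count alone. Comparing two bounds is then the same as comparing two observed percentages, with an unstated tolerance.

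What is at stake is the primary conclusion. The same data can be called similar because Fisher is non-significant, or not similar because the lower bounds lie far apart, and the choice can be made after unblinding. The plan leaves other choices open too:

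- On the Part 1 Day 57 selection, SAP 7.0 says "The evaluation will be based on unblinded data", and SAP 8.6 pools Part 1 subjects into this analysis.
- SAP 8.6 derives the threshold from "data after 3 doses of rF1V vaccine (or after 2 doses of rF1V" with CpG 1018, and marks that alternative as still to be determined.

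**Working it through.** **Inputs from the documents.** 85 evaluable of 90 planned per group, Parts 1 and 2 combined (SAP 4.0). Group 3 rate about 93%, from the earlier pooled analysis (SAP 4.0). 5% two-sided tests with no multiplicity adjustment (SAP 8.0).

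**Inputs assumed, because the plan gives none.** Lower-bound tolerances of 3, 5 and 10 points; margins of 5 to 15 points; true CpG rates of 80% to 93%.

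**1. The plan's own table.** Lower limit = Beta quantile (0.025; x, n-x+1); upper limit = Beta quantile (0.975; x+1, n-x); n=85.

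| Planned level | Count | Computed 95% CI | SAP Table 4-1 |
|---|---|---|---|
| 95% | 81/85 | 88.4% to 98.7% | 88% to 99% |
| 93% | 79/85 | 85.3% to 97.4% | 85% to 97% |
| 91% | 77/85 | 82.3% to 95.8% | 82% to 96% |

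The table reproduces. It gives single-group precision only.

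**2. One data set, two readings.** Take Group 3 at 79/85 (92.9%) and the CpG group at 70/85 (82.4%), a difference of (70-79)/85 = -10.6 points.

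- Fisher two-sided p=0.060, not significant. At 69/85 it becomes 0.038.
- Lower bounds are 72.6% and 85.3%, which are 12.7 points apart.
- The Miettinen-Nurminen 95% CI for the difference is -21.0 to -0.7 points. It is the set of δ with |z(δ)| ≤ 1.96, where z(δ) = (p1 - p2 - δ) / √{[p̃1(1-p̃1)/n1 + p̃2(1-p̃2)/n2] × N/(N-1)} and p̃1, p̃2 are the maximum-likelihood rates restricted to p̃1 - p̃2 = δ.

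Fisher read as a similarity test would pass this result, while the interval excludes zero.

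**3. How often each reading passes.** This is exact: sum Bin(x1; 85, p) × Bin(x2; 85, 0.93) over all pairs that meet the condition.

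| True CpG rate (Group 3 at 93%) | Fisher p>0.05 | Lower bound ≤5 points below | Lower bound ≤10 points below |
|---|---|---|---|
| 93% | 97.6% | 85% | 97.5% |
| 85% | 69% | 21% | 52.5% |
| 83% | 55% | 11.5% | 37.5% |
| 80% | 35% | 4% | 19.5% |

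With both arms at 93%, a 3-point tolerance passes 71%. At a true 83%, Fisher is non-significant while the CpG lower bound is more than 5 points below in 44% of trials, and more than 10 points below in 18%.

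**4. A rule on the difference.** Pass if the Miettinen-Nurminen 95% lower limit exceeds minus the margin, with 85 per arm. The margins are illustrations only.

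| True rates (CpG / Group 3) | 10 points | 12 points | 15 points |
|---|---|---|---|
| 93% / 93% | 66% | 79% | 94% |
| 90% / 90% | 55% | 70% | 88% |
| 83% / 93% | 2.4% | 5.5% | 16% |

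With Group 3 at 93% and the true difference exactly at the margin, the pass rate is 2.3% to 2.4% for each of the three. The one-sided 2.5% level therefore holds, given a fixed threshold.

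**5. Sample-size consequence.** Normal approximation for 80% power, both arms at 93%: n per arm = 2 × 0.93 × 0.07 × (1.96 + 0.84)² / margin². This gives 409 at 5 points, 103 at 10 and 46 at 15. The approximation is somewhat optimistic compared with the exact figures in step 4.

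**The case against.** The strongest reply has four parts.

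1. *The documents do contain a decision sentence, the one on lower bounds, and no text says that a non-significant Fisher test means similarity.* This is true, so the Fisher pass rates describe one possible reading and not a written rule. But the lower-bound sentence sits in the sample-size sections, has no number, and is not carried into the criterion in SAP 8.6. The 85% bound in SAP 4.0 is an expected value, not a pass mark.
2. *The conflict rates rest on invented tolerances.* They do. With both arms truly at 93%, the 5-point version still produces a conflict in about 13% of trials. The rates show how much depends on the missing number; they are not properties of the plan.
3. *This is a phase 2 trial sized for precision, and its other immunogenicity criteria use point estimates.* That is partly fair. Yet those criteria can be checked: a two-fold GMC ratio, and estimates that meet or exceed control. For this objective the plan says the effect is demonstrated and sets 5% tests, and Protocol 2.5 says the trial is powered to support a pre-EUA submission. SAP 8.0 reserves descriptive evaluation for Part 1.
4. *A margin makes the trial look underpowered.* It may, for a tight margin. That is a cost to state, not a reason to leave the criterion undefined.

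The separate report on the threshold does not close the gap, since it is described as covering only the threshold and its model.

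**Conclusion.** The concern holds. The primary criterion has no margin, no interval for the difference and no governing rule, so the same data can support opposite conclusions. At 85 per arm, a non-significant Fisher test tolerates an observed deficit of 10.6 points against 79/85, and occurs in 55% of trials when the true deficit is 10 points (83% against 93%). Under the lower-bound reading, two identical vaccines at 93% would pass between 71% and 97.5% of the time, depending only on whether the tolerance is 3 or 10 points.

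These figures assume independent binomial arms, 85 evaluable in each, a Group 3 rate of 93% and a threshold treated as fixed. The threshold is in fact estimated from trial data. The tolerances and margins are assumptions; the defect itself does not depend on them. Because this is a primary objective, it should be corrected before the final unblinding.

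**What to change.** In SAP 4.0 and 8.6, and Protocol 11.1 and 11.4:

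- Base the conclusion on the difference in predicted protection rate, CpG 1018 group at Week 8 minus Group 3 at Week 30, with a two-sided 95% CI by a score method such as Miettinen-Nurminen. Say whether site, the randomization stratum, is taken into account.
- Conclude similarity only if the lower limit lies above minus a margin that the sponsor justifies and fixes before the final unblinding and before the threshold is applied. The choice of margin is the sponsor's; none is recommended here.
- Replace the lower-bound sentence with this single rule, and keep the per-arm Clopper-Pearson intervals and the Fisher p-value as description.
- State the power at 85 per arm for the chosen margin.
- Disclose that the plan has Part 1 Day 57 data evaluated unblinded and then pooled into this analysis, and that the interval treats an estimated threshold as known.

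**Cost.** Text changes in both documents, with no added subjects or samples if the sponsor accepts the resulting power. That power is modest for a tight margin: 66% at 10 points with both arms at 93%, where 80% would need about 103 evaluable per arm, and about 409 at 5 points. Error control remains conditional on the threshold.
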